3.4.3 Exploratory Analysis

As the exploratory analysis, incidence of CMV disease or CMV viremia by Week 16 assessed by Endpoint data reviewers will be analyzed using the method described in Section 3.4.1. In addition, the below endpoints will also be analyzed.

- Incidence of CMV disease or CMV viremia by Week 28
- Incidence of CMV disease by Week 28
- Incidence of CMV viremia by Week 28

In addition, the Endpoint data reviewer findings will be listed by-patient.

As the supportive analysis, only criteria using the detection of ≥ 250 IU/mL in plasma measured by PCR analysis in central laboratory will be considered for the analysis of primary efficacy endpoint in Section 3.4.1. Non-responders will include all patients who have central CMV DNA assessments ≥ 250 IU/mL by Week 16. Patients who discontinue from the study prior to Week 16 in the absence of central CMV DNA assessments ≥ 250 IU/mL will be considered as non-responders.

3.4.4 Subgroup Analysis

Subgroup analysis will be performed to explore the consistency of the treatment effect for subgroups.

Statistical analysis of the primary efficacy endpoint and selected secondary efficacy endpoints will be provided within each category of the following variables if the data allows:

- Country (United States, Japan)
- Weight group (< 100 kg, ≥ 100 kg)
- ABO compatibility (Compatible, Incompatible)
- Induction therapy (Yes, No)
- Donor status (Deceased, Living)

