2.2.4 Sample Size Determination

A total sample size of approximately 108 patients is planned for the study, with a 1:1 randomization ratio for 6 mg/kg NPC-21 versus placebo and another 12 patients for high-level dose of 12 mg/kg NPC-21 (4:1:4 randomization ratio for 6 mg/kg NPC-21, 12 mg/kg NPC-21, or placebo). The sample size calculation is based on the modified Intent-to-Treat (mITT) Population from the first dose of NPC-21 through Week 16 for the occurrence of CMV disease (CMV syndrome or tissue-invasive CMV disease) or CMV viremia (defined as the detection of ≥ 250 IU/mL in plasma measured by PCR analysis in central laboratory or meets the local criteria for CMV viremia measured by PCR analysis or antigenemia testing) primary endpoint. Assuming an early discontinuation rate of 15%, approximately 48 patients each in the 6 mg/kg NPC-21 and placebo arms are needed with a 2-sided significance level of 0.05 and a power of 80% to detect a difference between NPC-21 at a predicted incidence rate of CMV disease (CMV syndrome or tissue-invasive CMV disease) or CMV viremia of 30% versus 60% for placebo. In addition, a sample size of 12 patients for the 12 mg/kg NPC-21 arm is considered adequate for the planned exposure-response analysis.

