3.4.1 Primary Efficacy Analysis

The proportion of patients with the occurrence of CMV disease (CMV syndrome [see Appendix C of the protocol for definition of CMV syndrome] or tissue-invasive CMV disease [see Appendix D of the protocol for definitions of CMV disease]) or CMV viremia (defined as the detection of ≥ 250 IU/mL in plasma measured by PCR analysis in central laboratory or meets the local criteria for CMV viremia measured by PCR analysis or antigenemia testing) by Week 16 will be summarized by treatment group.

The 2-sided 95% exact Clopper-Pearson confidence intervals of the proportions will be provided. For any two treatment groups, the proportion difference and 95% unstratified Miettinen-Nurminen (score) confidence limits will be presented.

Comparisons across placebo and 6 mg/kg NPC-21 treatment group will use logistic regression analysis with stratification factor of region (United States or Japan) as a covariate

Non-responders will include all patients who develop CMV disease or CMV viremia. In principle, patients who discontinue from the study prior to Week 16 in the absence of CMV disease or CMV viremia will be considered as non-responders. If warranted under special circumstances, a patient who discontinues from the study prior to Week 16 may be discussed with the medical expert to determine status as a responder or non-responder. If this occurs, the rationale for considering the patient as a responder will be finalized before database lock and documented in this SAP. Sensitivity analysis may be performed to assess the impact of these patients on analysis results.

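### The subgroup section aims at consistency of effect but plans only within-category analyses; an exploratory interaction estimate with its interval would address that aim directly (low priority)

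*SAP*

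**What the plan says.** SAP 3.4.4 gives the purpose: "Subgroup analysis will be performed to explore the consistency of the treatment effect for subgroups". The method follows: "Statistical analysis of the primary efficacy endpoint and selected secondary efficacy endpoints will be provided within each category" of Country, weight group, ABO compatibility, induction therapy and donor status, where the data permit. The selected secondary endpoints are not named.

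The analysis to be repeated is in SAP 3.4.1. It has two parts. One is descriptive: proportions with exact 95% intervals, and differences in proportions with unstratified 95% score limits. The other is a test: "Comparisons across placebo and 6 mg/kg NPC-21 treatment group will use logistic regression analysis with stratification factor of region" as covariate. The Statistics section of the protocol sets tests at two-sided 0.05.

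Neither protocol 10.2.1, the SAP nor the SAP addendum plans a treatment-by-subgroup interaction, and none gives a rule for deciding whether categories agree.

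**The concern.** Consistency is a question about the difference between two effects. Separate results in each category do not estimate that difference. Because the primary analysis includes a test, repeating it by category will by default produce a p-value in each of ten categories. A reader may then compare the p-values and take significant here, not significant there as evidence that the effects differ. In categories this small, that pattern is common when the effects are identical.

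There is also a specification detail. Within the United States or within Japan the region covariate is constant, so the SAP 3.4.1 model cannot be repeated there unchanged.

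At stake is the interpretation of exploratory output, not the primary comparison.

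**Working it through.** **Inputs.** From SAP 2.2.4: event rates "CMV viremia of 30% versus 60% for placebo"; "approximately 48 patients each in the 6 mg/kg NPC-21 and placebo arms are needed"; two-sided 0.05; 80% power; 15% early discontinuation. The documents give no category sizes, so the splits below are assumptions, applied equally to both arms.

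**1. The plan's own figure.** With unpooled variance, n = (1.960 + 0.842)² × (0.30×0.70 + 0.60×0.40) / 0.30² = 7.849 × 0.45 / 0.09 = 39.2, so 40 per arm. Then 40 / 0.85 = 47.1, so 48. This matches the SAP.

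**2. Reading by significance.** Assume the same 30% versus 60% effect in both categories and 48 per arm. Let a and b be the exact powers of the uncorrected chi-square test in the two categories. The probability that exactly one is significant is a(1−b) + b(1−a). For the even split this is 2 × 0.590 × 0.410 = 0.484.

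| Split | Patients per arm | Power a / b | Exactly one significant | Both significant |
|---|---|---|---|---|
| 50:50 | 24 / 24 | 0.590 / 0.590 | 48.4% | 35% |
| 67:33 | 32 / 16 | 0.713 / 0.412 | 53.8% | 29% |
| 75:25 | 36 / 12 | 0.727 / 0.357 | 56.5% | 26% |
| 90:10 | 43 / 5 | 0.810 / 0.169 | 70.5% | 14% |

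Sensitivity, using normal-approximation power from an even split to 90:10:
- 48 per arm: 49% to 72%.
- 41 evaluable per arm: 50% to 68%.
- 15% discontinuations counted as non-responders, giving rates 0.30 + 0.15×0.70 = 40.5% and 0.60 + 0.15×0.40 = 66%: 49% to 63%.

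Across five factors assumed independent, simulation gives at least one discordant pair in 83% of trials (all splits even) to 93% (all 80:20).

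**3. Reading by risk differences and intervals.** At an even split each category's risk difference has SE √(0.45/24) = 0.137, and the difference between the two has SE √(2 × 0.45/24) = 0.194.
- A given estimate lies outside the other category's 95% CI if the gap exceeds 1.96 × 0.137 = 0.268. That is 0.268/0.194 = 1.39 standard errors, a probability of about 17%.
- The two CIs fail to overlap if the gap exceeds 0.537, or 2.77 standard errors: under 1%.
- At least one category shows an effect in the wrong direction in about 3%.

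The first of these readings worsens with imbalance. At 75:25 the SEs are √(0.45/36) = 0.112 and √(0.45/12) = 0.194, and the SE of their difference is 0.224. The smaller category's estimate then lies outside the larger category's CI when the gap exceeds 1.96 × 0.112 / 0.224 = 0.98 standard errors, about 33%. Non-overlap stays under 1%.

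**4. What an interaction estimate would deliver.** The variance of a log odds ratio with n per arm is 1/(0.24n) + 1/(0.21n). For n = 24 this is 0.174 + 0.198 = 0.372. The log ratio of two such odds ratios has SE √(2 × 0.372) = 0.86, twice the main-effect SE of 0.43. Its 95% CI is the estimate times or divided by exp(1.96 × 0.86) ≈ 5.4, and about 8.3 at 80:20. Power to detect an interaction as large as the whole planned effect (log 3.5 = 1.25) is about 31% at an even split and 21% at 80:20. Under an identical effect, a 0.05-level interaction test would flag a factor in about 4.5% of trials at an even split and 3% at 80:20.

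**The case against.** The strongest reply is that the roughly one-half figure is the error rate of a reading rule that the SAP does not contain. A reader might infer that consistency is to be judged by which categories reach significance. SAP 3.4.4 says only that consistency will be explored and that analyses will be provided. SAP 3.4.1 already supplies risk differences with 95% limits, and comparing those is an ordinary and far less misleading way to look. This stands, and the figure is conditional for that reason.

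Two other tempting readings go too far. One is that the likely result is a false message that the drug works in only one region. That needs the planned effect to be true, a significance-only reading and a split that the documents do not give; even then the even-split figure is 48%. The other is that United States versus Japan is the most important factor: the SAP does not rank the five.

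The Country model problem is small. A constant covariate drops out, the treatment estimate remains defined, and the score limits are unstratified anyway.

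An interaction estimate is also imprecise, and it sits on the odds-ratio scale while the display uses risk differences. The two can disagree: 60% to 30% and 40% to 10% share a risk difference of 30 points, but the odds ratios are 0.29 and 0.17. This limits what the addition can show. It does not alter the fact that nothing now planned estimates the difference between categories.

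**Conclusion.** The point holds as a modest one. The stated aim is consistency, and no between-category estimate is planned. Whether the output misleads depends on how it is read. By significance, an identical effect gives a discordant pair in about 48% (even split) to about 70% (90:10) of trials. By the planned risk differences and intervals at an even split, the figure is about 17% or under 1%, depending on the reading. These figures assume the design rates, 48 per arm and category splits chosen for illustration.

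The analyses are exploratory, in a Phase 2 trial. The primary comparison, the sample size and the error control are unaffected. Priority: low, a cheap improvement.

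**What to change.** - Keep the within-category risk differences and 95% CIs as the main display, and state that within-category p-values are not used to judge consistency.
- For each factor, where the data allow, report the treatment-by-factor interaction estimate with 95% CI from one logistic model for 6 mg/kg versus placebo with region as covariate. State that this is on the odds-ratio scale.
- For Country, estimate the treatment-by-region interaction in the full model, and drop the constant region covariate from the within-country models.
- Label all of this exploratory, with no pass/fail interaction test; power of about 20% to 30% even for a difference as large as the planned effect would not support one.

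The cost is a few lines of text and five extra models. The intervals will be wide. The addendum records database lock on 30 March 2023, so an addition after that date should be documented as post-lock.

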3.5 Analysis of Pharmacokinetic

Serum concentrations of NPC-21 will be summarized using descriptive statistics. Geometric mean and geometric coefficient of variation will also be provided. For the calculation of descriptive statistics, BLQ values will be set to zero and missing data will not be imputed. 2-hour post-dose samples collected outside the sampling window of 2 hours +/- 30 minutes after infusion start may be excluded from the calculation of descriptive statistics. Plots of mean concentrations of plasma NPC-21 versus time will be generated for each dose group and scheduled visit.

In addition, analysis of the concentration data as part of population-PK modeling will be described in a separate PK Analysis Plan and reported separately.

The PK listing will be provided.

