4.3 Withdrawal Criteria

Patients may be discontinued from study drug for any of the following reasons:

- The patient no longer meets all inclusion criteria or meets any exclusion criteria and is found to be ineligible for participation through procedures (eg, medical examinations) performed after Randomization.
- Occurrence of any medical condition or circumstance that exposes the patient to substantial risk and/or does not allow the patient to adhere to the requirements of the protocol.

- Any SAE, clinically significant adverse event, severe laboratory abnormality, intercurrent illness, or other medical condition that indicates to the Investigator that continued participation is not in the best interest of the patient.
- Pregnancy.
- Requirement of the following therapy:
 - CMV hyperimmune globulin (eg, CytoGam®).
 - IVIg.
 - Plasmapheresis.
- Patient failure to comply with protocol requirements or study-related procedures and the Investigator considers it inappropriate to administer the study drug.
- Initiation of Rescue Phase.

Patients who discontinue study drug for any reason should be followed per the study schedule of events until the end of study participation.

Participation of a patient in this clinical study may be discontinued for any of the following reasons:

- The patient withdraws consent or requests discontinuation from the study for any reason.
- Termination of the study by the Sponsor or the regulatory authority.
- If a patient develops COVID-19 and is unable to continue with study visits and observations, the patient should be discontinued from the study and standard of care CMV treatment should be initiated, if necessary. If COVID-19 treatment will be provided to the patient, the Investigator should notify the Medical Monitor prior to study discontinuation, if possible. All patients should be followed for safety and resolution of COVID-19 infection. Patients who are able to complete study-related visits as an outpatient or via home healthcare services (United States only) or are inpatient and can receive study treatment will be allowed to continue to participate in the study if they do not receive any experimental treatments for COVID-19.

In the case of patients lost to follow-up, attempts to contact the patient must be made and documented in the patient's medical records.

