5.5.3 Study Drug Administration

Patients randomized to NPC-21 will be administered a dose of 6 or 12 mg/kg of actual body weight (at Screening) via an approximately 60-minute (5 mL/minute) intravenous infusion on Day 1 and at Weeks 4, 8, and 12.

Patients randomized to placebo will be administered approximately 300 mL of normal saline via an approximately 60-minute (5 mL/minute) intravenous infusion on Day 1 and at Weeks 4, 8, and 12.

Patients will be asked to remain at rest in the supine position, in principle, during study drug administration and should remain resting, in principle, from the end of study drug administration until the tests scheduled within 1 hour after study drug administration.

If an adverse event, especially an infusion reaction, occurs during study drug administration and the Investigator deems it necessary, deceleration, suspension, or resumption of study drug administration is allowed. In case of a Grade 2 infusion reaction, study drug administration will be suspended and study drug administration will be resumed (flow rate will be 2.5 mL/minute) after recovery from the symptoms by treatments. In the case of a Grade 3 or higher infusion reaction, study drug administration will be terminated. Details will be entered in the eCRF. Refer to the Pharmacy Manual for more information.

The day of administration as well as the administration start and end time will be entered in the eCRF.

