6.6 Rescue Phase

After first study drug administration, patients who develop detectable CMV disease (CMV syndrome [see Appendix C for definition of CMV syndrome] or tissue-invasive CMV disease [see Appendix D for definitions of CMV disease]) or CMV viremia (defined as the detection of ≥ 250 IU/mL in plasma measured by PCR analysis in central laboratory or meets the local criteria for CMV viremia measured by PCR analysis or antigenemia testing) can enter the Rescue Phase of the study and be treated by anti-CMV agents per local standard of care until the patient is negative for CMV viremia, has recovered from CMV disease, or up to Week 28, whichever comes first. When this rescue therapy is completed, the Rescue Phase is terminated at least 4 Study Weeks after the last study drug administration and all Week 28 procedures will be performed as per Section 6.7 Early Termination Visit and Withdrawal Procedures.

Note: Collection of blood samples for serum NPC-21 concentration measurement at Weeks 4, 8, and 12 during the Rescue Phase will be handled in the same manner as visits without study drug administration.

Note: If the patient is negative for CMV viremia or has recovered from CMV disease before 4 Study Weeks have passed following last study drug administration, weekly scheduled visits are not required. The Rescue Phase visits may be conducted by home healthcare services (United States only). The Rescue Phase procedures may be performed at the next scheduled visit after detecting CMV viremia or CMV disease with or without anti-CMV agents per local standard of care. Some Investigators may prescribe anti-CMV agents (eg, VGCV) in advance and instruct the patient to start taking the drug as soon as possible for safety if the disease or viremia develops. If this is the case, the Rescue Phase procedures may be performed at the next scheduled visit.

The following procedures will be performed upon entering the Rescue Phase:

- Record the rescue in IRT.
- Record concomitant medications.
- Record the date and reason for entering the Rescue Phase.
- Perform complete physical examination.
- Collect blood sample for CMV DNA analysis by the central laboratory.
- Collect blood samples that will be stored for screening for resistant strains analysis.
- Perform EQ-5D-5L.
- Record adverse events.

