3.2.4 Pharmacokinetic Population

The Pharmacokinetic (PK) Population will include all patients who receive any amount of study drug (6 mg/kg NPC-21, 12 mg/kg NPC-21, or placebo) and have evaluable PK data. The PK Population will be used for the PK analyses and exposure-response analyses.

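### SAP 3.5 averages NPC-21 concentrations by visit without regard to doses received, so trough means from Week 8 onward mix dosed patients with patients who stopped drug at rescue

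*SAP*

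**What the plan says.** SAP 3.5 summarises serum concentrations with descriptive statistics, geometric means and geometric coefficients of variation, and adds that "Plots of mean concentrations of plasma NPC-21 versus time will be generated for each dose group and scheduled visit". Its only rule for leaving out a measured sample concerns timing: "2-hour post-dose samples collected outside the sampling window of 2 hours +/- 30 minutes after infusion start may be excluded". The PK Population in SAP 3.2.4 "will include all patients who receive any amount of study drug (6 mg/kg NPC-21, 12 mg/kg NPC-21, or placebo) and have evaluable PK data"; neither document defines evaluable.

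Protocol 4.3 lists "Initiation of Rescue Phase" among the reasons to stop study drug, and continues: "Patients who discontinue study drug for any reason should be followed per the study schedule of events until the end of study participation". Protocol 6.6 says that PK sampling at Weeks 4, 8 and 12 "during the Rescue Phase will be handled in the same manner as visits without study drug administration". Protocol 9.12 runs PK sampling to Week 28. Protocol 6.6 also lets the Rescue Phase end once rescue therapy is complete and at least 4 Study Weeks have passed since the last dose.

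SAP 3.3.7, by contrast, does leave out patients who have withdrawn from treatment or entered rescue when it reports the proportion dosed at each visit. SAP 3.5 has no matching rule.

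On infusions, Protocol 5.5.3 says that after a Grade 2 reaction "study drug administration will be resumed (flow rate will be 2.5 mL/minute) after recovery from the symptoms by treatments".

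**The concern.** A patient rescued after one dose and a patient who received all four can both contribute a sample labelled Week 16, 6 mg/kg. The first is 16 weeks past the last dose and the second is 4 weeks past it. Averaging them gives a figure that describes neither, and its composition depends on how many patients had CMV events, when, and how long rescue lasted.

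These tables and plots are the only PK output that the SAP itself specifies. A reader will take the Week 8, 12 and 16 values as the troughs that the regimen achieves, and part of any shortfall would come from patients who were no longer being dosed.

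There is a lesser point on the 2-hour sample. It is timed from the start of infusion, so after a suspended and slowed infusion it may be drawn before the infusion has ended and still be summarised as a post-dose value.

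**Working it through.** **Inputs**
- Half-life 612.30 to 790.41 h, that is 25.51 to 32.93 days (Protocol 1.1).
- Doses on Days 1, 29, 57 and 85.
- Event rate by Week 16 of 30% on 6 mg/kg (Protocol 10.2.7, SAP 2.2.4).
- Assumptions: linear kinetics with single-exponential decline; events spread evenly over 16 weeks, so 7.5% in each 4-week interval; every event leads to rescue; exposure unrelated to events.

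**The plan's own figure.** The documents give no PK summary figure to reproduce. The 30% comes from the sample size calculation, which does reproduce. With unpooled variance, (1.960 + 0.842)² × (0.30×0.70 + 0.60×0.40)/0.30² = 39.2, so 40 per arm, and 40/0.85 = 47.1, so 48.

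**Step 1: where mixing can start.** No patient can have missed a dose before the Day 29 pre-dose sample, so rescue cannot affect it. The first pre-dose visit after rescue begins is also still a true 4-week trough. The first trough that can be mixed is Week 8. By the same logic the mid-interval Week 6 sample can be mixed too.

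**Step 2: off-drug level as a share of the on-schedule trough.** Let r = exp(−28 × ln2 / half-life in days), which is 0.467 (shorter half-life) or 0.555 (longer). The on-schedule Week 16 trough is proportional to 1 + r + r² + r³ = 1.788 or 2.033. Patients with 1, 2 or 3 doses have r³, r² + r³, or r + r² + r³.

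| Visit | 1 dose | 2 doses | 3 doses |
|---|---|---|---|
| Week 8 | 0.318-0.357 | on schedule | – |
| Week 12 | 0.130-0.165 | 0.407-0.463 | on schedule |
| Week 16 | 0.057-0.084 | 0.179-0.235 | 0.441-0.508 |

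**Step 3: pooled mean.** Patients with an event in the fourth interval have had all four doses. At Week 16 the off-drug share is therefore 3 × 7.5% = 22.5% if all are still sampled. The pooled mean relative to the on-schedule mean is:
- shorter half-life: 0.775 + 0.075 × (0.057 + 0.179 + 0.441) = 0.826, or 17.4% low;
- longer half-life: 0.775 + 0.075 × (0.084 + 0.235 + 0.508) = 0.837, or 16.3% low.

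If only a share q of rescued patients is still sampled, 0.075 becomes 0.075q and the sum is divided by 0.775 + 0.225q. The same calculation for each visit gives:

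| Rescued patients still sampled | Week 8 | Week 12 | Week 16 |
|---|---|---|---|
| All | −4.8 to −5.1% | −10.3 to −11.0% | −16.3 to −17.4% |
| Half | −2.5 to −2.7% | −5.6 to −5.9% | −9.2 to −9.8% |
| A quarter | −1.3 to −1.4% | −2.9 to −3.1% | −4.9 to −5.2% |

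If instead all 30% had their event in the first dosing interval and all stayed sampled, the shortfall would be 19-20%, 25-26% and 28% at Weeks 8, 12 and 16.

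**Step 4: geometric mean.** The pooled-to-on-schedule ratio is the product of the step 2 ratios, each raised to its share of the sample. With all sampled at Week 16 this is (0.057 × 0.179 × 0.441)^0.075 = 0.667, or (0.084 × 0.235 × 0.508)^0.075 = 0.708. That is 29-33% low. With a quarter sampled it is 10-12% low.

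**Step 5: 2-hour sample.** For about 300 mL started at 5 mL/min, a reaction at x minutes, a suspension of s minutes and resumption at 2.5 mL/min, the infusion ends at x + s + (300 − 5x)/2.5 = 120 + s − x minutes. It is still running at 2 hours only if s exceeds x. With x = 10 and s = 15 to 30 it ends at 125-140 minutes. At 2 hours, 12.5-50 mL of the 300 mL is outstanding, so 83-96% of the dose is already in.

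**The case against.** Several arguments on the other side stand, and they limit the point.

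- **Dose rationale.** A reader might infer that the check on the 19 µg/mL target is compromised. Protocol 5.2 makes its simulation claim for the Day 29 trough only, and rescue cannot touch that value.
- **Exit from rescue.** A reader might also infer that all rescued patients stay on schedule to Week 28. Protocol 6.6 lets them leave once therapy is complete and 4 Study Weeks have passed since the last dose, and does not require weekly visits for those who clear sooner. The 16-17% figure is thus the top of the range under even event timing.
- **6 versus 12 mg/kg.** A distorted dose comparison might be inferred as well. The documents give no event rate for 12 mg/kg, and with equal event patterns and linear kinetics the proportional bias cancels in the ratio. That reading is unsupported.
- **Reach.** Population-PK and exposure-response analyses sit in separate plans, which may use actual dosing records. No test or decision rule in the SAP uses the by-visit means.
- **Evaluable data.** The undefined term could in principle exclude off-drug samples, but no document says that it does.
- **Selection.** Restricting the only table to fully dosed patients would select largely on having had no earlier event. If low concentration leads to breakthrough, that table would overstate exposure. An all-samples summary is a legitimate description of what was achieved, so it should stay.
- **Infusion timing.** At the nominal 2 hours the problem needs a suspension longer than the time before the reaction, and most of the dose is in by then. It is minor.

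None of this supplies the missing rule. SAP 3.3.7 shows that the distinction was recognised for another summary.

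**Conclusion.** The point holds for the descriptive PK tables and plots at troughs from Week 8 onward. Followed as written, SAP 3.5 pools off-drug samples with regimen troughs, and the result is biased downward as a description of the regimen. Under even event timing and a 30% event rate, the Week 16 mean on 6 mg/kg is about 5% to 17% low, depending on whether a quarter or all of the rescued patients are still sampled. The geometric mean moves more.

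The missing rule and the direction are clear; the size is not fixed by the documents. It rests on the Phase 1 half-life applying to transplant recipients, on single-exponential decline (Protocol 1.1 calls elimination biphasic), on every event leading to rescue (the protocol says patients can enter it), on event timing, and on a rescue duration that is not stated. Nothing here bears on the efficacy analysis.

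**What to change.** In SAP 3.5:

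1. Flag each PK sample by whether every scheduled dose due before it was received in full.
2. Present the by-visit tables and plots for on-schedule samples.
3. Present samples taken after a missed dose, a terminated infusion or rescue separately, by time since last dose.
4. Keep an all-samples by-visit version alongside.
5. State that the on-schedule summary is conditional on no earlier event or discontinuation, and may overstate exposure if low concentration leads to breakthrough.
6. Flag any nominal 2-hour sample drawn before the recorded end of infusion, and do not summarise it as a post-dose value (minor).

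The cost is SAP wording, a programming flag and additional displays. Dosing dates and infusion start and end times are already collected (Protocol 5.5.3). The downsides are fewer patients per visit in the on-schedule table and the selection caveat in item 5. The database was locked on 30 March 2023 and a SAP addendum followed on 15 May 2023, so any change should be documented in the same way and labelled as made after lock.
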